CGI-S	Exploratory	
• A single item, 7-point Likert scale to measure the overall severity of the patient's current clinical presentation and symptomatology. (Busner et al., 2007)• The investigator will rate the participant's severity of illness based on clinical interviews and assessments relative to their experience with other patients with the same diagnosis.• Response choices include 0 (not assessed) and range from 1 (Normal, not at all ill) to 7 (Among the most extremely ill patients).• The CGI-S will be administered at baseline, Week 4, and Week 8.
CGI-I	Exploratory	
• A single item, 7-point Likert scale to measure the overall improvement in the patient's condition at the end of treatment. (Busner et al., 2007)• The investigator will rate whether the participant's total improvement was due entirely to the intervention.• Response choices include 0 (not assessed) and range from 1 (very much improved) to 7 (very much worse).• The CGI-I will be administered at Week 4 and Week 8.
PGI	Exploratory	
• The Patient Global Impression scale (PGI), also known as Subject Global Impression (SGI), is the PRO counterpart to the Clinical Global Impressions scale, (CGI), which was published in 1976 by the National Institute of Mental Health (US). (Snyder et al., 2020)• Consists of one item based on the CGI and is adapted to the patient.• The PGI mainly measures change in clinical status (PGI-C) but can also measure disease severity (PGI-S) or disease improvement (PGI-I).• PGI-S is administered at baseline, Week 4, and Week 8; PGI-C is only administered at Week 4 and Week 8.
Client Satisfaction Questionnaire	Other/ Exploratory	
• Participants will be prompted to complete an 8-question Client Satisfaction Questionnaire (CSQ) to assess their level of satisfaction with WB001 vs. ED001 applications.• The CSQ will be administered at Week 8.

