9.3 EXPLORATORY ENDPOINT(S)

Exploratory analyses will be conducted in the ITT population. Given the ordinal nature of the remaining efficacy endpoints (CGI-I; CGI-S; PGI-C; PGI-S), the analysis plan for HAM-D will be modified to compare treatment arms by the odds selecting a given ordinal category at Week 8 controlling for other factors in the model. Models will be fit via PROC GLIMMIX.

Additionally, the MMRM approach to analyzing the difference between arms will be supplemented via a latent class analysis approach that uses a multiple indicator linear growth model (LGM) for categorical outcomes. More details about the analyses can be found in the SAP.

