APPENDIX 3: SCHEDULE OF EVENTS

Mechanism to Execute	Epochs	Screening/Baseline** Day 1 must be completed on same day	Week 4 Day 28 ±3	Week 8 (EOT/ET) Day 56 ±3
Clinical Outcome Assessments			Intervention Period	
In-person by site staff	Randomization *After the following assessments are completed and patient meets all I/E Criteria	X		
In-person by blinded site staff via tablet or paper copy	Informed Consent	X		
In-person by blinded site staff for input in EDC	Inclusion/Exclusion Criteria	X		
In-person by blinded site staff for input in EDC	Demographics	X		
In-person by blinded site staff for input in EDC	Previous Medications	X		
In-person by blinded site staff for input in EDC	Psychiatric History	X		
In-person by blinded site staff/PI via tablet	SCID-5-CT^{a, e}	X		
Hybrid by blinded site staff/PI for input in EDC	Concomitant Medications and Therapy *Post randomization, will rely on self-report from participant on continued TAU	X	X	X
Hybrid by blinded site staff/PI for input in EDC	Pregnancy History and Status *Post randomization, will rely on self-report from participant on pregnancy status	X	X	X
Virtual by blinded CIR	HAM-D17^c *Primary endpoint is HAM-D 6 derived from HAM-D17	X	X	X

Sponsor Name: Woebot Health

Protocol Number: WB001-001

Hybrid by blinded site staff/PI	C-SSRS^a *Safety endpoint and will be administered virtually by PI if safety event is flagged and confirmed	X	X	X
Self-report via link	EPDS^b *If safety flag is raised due to score of >2 on item #10, EPDS, PI/site staff are notified immediately for review, and action, if needed	X	X	X
Self-report via link	PHQ-9^b *If safety flag is raised due to score of ≥ 2 on item #9, PHQ-9PI/site staff are notified immediately for review and action	X	X	X
Self-report via link	GAD-7^b	X	X	X
Hybrid by blinded site staff/PI into EDC	CGI-S^a	X	X	X
Virtual by blinded site staff/PI into EDC	CGI-I^a		X	X
Self-report via link	PGI- S^b	X	X	X
Self-report via link	PGI- C^b		X	X
Self-report via link	MIBS^b	X	X	X
Self-report via link	Healthcare Utilization	X	X	X
Self-report via link	Program Assignment Assessment (Blinding)			X
Hybrid by blinded site staff/PI into EDC	AEs/SAEs Assessment^a *Includes confirming no recent hospitalizations for mental health-related incidence	X	X	X
Self-report via link	CSQ-8^b			X
Virtual by blinded PI	Escalation Trigger Follow-Up		X ^d	

Sponsor Name: Woebot Health

Protocol Number: WB001-001

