AE = adverse event; BL = baseline; CGI-I = Clinical Global Impression of Improvement; CGI-S = Clinical Global Impression of Severity; C-SSRS = Columbia-Suicide Severity Rating Scale; CSQ = Customer Satisfaction Questionnaire; EOT = end of treatment; EPDS = Edinburgh Postnatal Depression Scale; ET= Early Termination visit; GAD = Generalized Anxiety Disorder Questionnaire; HAM-D = Hamilton Depression rating scale; MIBS = Mother-to-Infant Bonding Scale; PHQ = Patient Health Questionnaire; PGI-C = Patient Global Impression of Improvement of Change; PGI-S = Patient Global Impression of Disease Severity; SCID-5-CT = Structured Clinical Interview for DSM-5 - Clinical Trials Version; Hybrid = indicates conducted in-person at BL and virtual by participant post-randomization through link; CIR = Central Independent Rater;

^a These assessments will be administered by blinded investigator or qualified designee (e.g., sub-investigator, or dually qualified site staff).

^b These assessments will be self-administered and completed independently by participant s as a link (± 3 days of visit date)

^c Will be administered by a CIR

^d Any confirmed Escalation trigger through the following three scenarios will result in PI-administered C-SSRS:

- [REDACTED]
- [REDACTED]
- [REDACTED]
- [REDACTED]
- [REDACTED]

^e Only includes modules for major depressive disorder (MDD), current and lifetime diagnosis of a psychotic disorder including postpartum psychosis and Schizophrenia, bipolar disorder, homicidal or infanticidal ideation, and history of drug and/or alcohol

AE/SAE collection will begin at the time ICF is signed. AEs/SAEs should be recorded until the EOT visit.

*Note: the HAM-D will be administered as the Structured Interview Guide for the Hamilton Depression Rating Scale – 17 item version (SIGH-D 17-item HAM-D) to derive the HAM-D6 as the primary endpoint

**Final Screening and Baseline visit assessments must be completed on the same day.

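### The CGI-I instruction asks raters to judge cause, which contradicts the scale's own definition, its anchors and the planned ordinal analysis

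*Combined protocol and SAP*

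**What the plan says.** The CGI-I row of the assessment table in Section 5.2 makes three statements about what is rated. The scale is a "7-point Likert scale to measure the overall improvement in the" patient's condition. The investigator is to rate whether the participant's "total improvement was due entirely to the intervention". The coding is then given as "Response choices include 0 (not assessed) and range from 1 (very much improved) to 7 (very much worse", with the parenthesis closed after the last word.

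On timing, the row states: "The CGI-I will be administered at Week 4 and Week 8". Appendix 3 gives the mode and rater as "Virtual by blinded site staff/PI into EDC", and its footnote a adds: "These assessments will be administered by blinded investigator or qualified designee". Table 2 in Section 3.5 lists the PI and the site staff who do assessments as blinded at every event.

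Section 9.3 treats the CGI-I as an exploratory ordinal endpoint and will "compare treatment arms by the odds selecting a given ordinal category at Week 8", controlling for other factors in the model.

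**The concern.** The middle statement in the row does not belong with the other two. A question about whether improvement came wholly from the intervention calls for a yes, a no or a share. The definition and the anchors ask how much the patient has changed, and in which direction.

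The design makes the causal question hard to answer. Under Section 3.1 both arms receive TAU, which may include medication or psychotherapy, so a participant can improve for reasons unrelated to the app. The rater does not know which app was assigned.

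At stake is whether the CGI-I measures what the protocol says it measures. If some raters follow the sentence and others follow the anchors, across up to 25 sites, the same clinical course can receive different scores.

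**Working it through.** No figure in the plan depends on this wording, so the check sets the provisions side by side.

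**1. What each element of the row can record.**

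| Clinical course | Score under the anchors | Answer under the instruction |
|---|---|---|
| Improved, rater credits the app | An improved category | Yes |
| Improved, rater credits TAU | The same improved category | No, or not entirely |
| Unchanged | The middle of the scale | No improvement to attribute |
| Worse | A worse category | No improvement to attribute |

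The two readings separate in the second line: equal improvement gets equal scores under the anchors but different answers under the instruction. In the last two lines the instruction has no answer at all. None of the codes means due or not due to the intervention, and the 0 code only records that no assessment was made.

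**2. Comparison with the neighbouring row.** For the CGI-S, Section 5.2 asks for severity relative to other patients with the same diagnosis and gives anchors of severity. Instruction and anchors agree there. The mismatch is specific to the CGI-I.

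**3. What the rater can know.** Section 3.5 uses the word intervention for the assigned app. Table 2 and Appendix 3 keep the rater blind to it. A literal reading therefore asks for the causal share of an app that the rater cannot identify, alongside TAU that everyone receives.

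**4. What the analysis needs.** The Section 9.3 model compares arms on ordered categories. That is sensible if the categories grade change. It has no clear meaning if some scores grade change and others grade attributed change.

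**5. Effect on the comparison if raters stay blind.** Randomization balances TAU between arms on average, and a blinded rater cannot discount by arm. Some improvement that WB001 did produce could be credited to TAU and marked down, and there is less of that improvement to lose in the control arm. Mixed use of the sentence and the anchors adds disagreement between raters. Both probably pull the contrast toward no difference. A sharper contrast would need raters who can separate the app's effect from that of TAU, and the design gives them no means to do so.

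**6. How many ratings enter the comparison.** The planned sample is 210 (Synopsis).
- Week 8 ratings: 210 × 1 = 210, or 210 / 2 = 105 per arm under 1:1 allocation.
- Ratings collected at both visits: 210 × 2 = 420.

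Section 9.3 specifies the between-arm comparison at Week 8 only, so about 210 is the relevant number. Missed visits would lower it, and the sample size re-estimation in Section 9.9 could change it. It counts ratings exposed to the wording and does not measure distortion.

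**The case against.** The strongest reply is that the table only summarizes the assessments. Section 5 refers to a separate Protocol Supplement for response options and scoring. That document and the rating form are not available here and may carry correct wording. The row also states the right construct and the right anchors, so a trained rater could ignore the stray sentence. This stands as a limit: the harm depends on the form or training repeating the sentence, or on raters taking the protocol literally. It does not remove the defect, because investigators sign to conduct the study according to this protocol, and a correct form would then disagree with it.

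It can also be said that the word intervention is used loosely. Section 5.1 applies it to concomitant treatment as well. The app is the likelier meaning here, but not the only one. On either meaning the sentence still asks about cause.

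A reader might infer something stronger: that the wording biases the CGI-I odds ratio in favour of WB001 and leads site raters to guess allocation. The documents do not support that. The raters are blinded. Both arms use an app, and Section 3.1 has both presented to participants in the same terms. A rater could form a view on whether the app helped without deciding which app it was. What remains is a possible route. Section 3.6 accepts that accidental unblinding may occur in discussions with the PI and site staff, and relies on the central raters to protect the primary endpoint. The CGI-I is rated by the PI and site staff, so it lacks that protection. Nothing shows that such unblinding happens, or how often.

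**Conclusion.** The point holds as an internal contradiction in the protocol text: the CGI-I instruction does not fit the row's own definition, its anchors or the Section 9.3 analysis, and nothing else in the documents corrects it.

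The consequence is small. If the wording reaches raters and they follow it, the likely result is inconsistency between raters and some attenuation of one exploratory comparison, on up to about 210 Week 8 ratings. Bias between arms needs the further condition that raters suspect allocation. Neither effect can be sized from the documents.

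A reader might take all 420 ratings as affected in the analysis, or extend the point to the main result. Neither follows. The specified comparison is at Week 8, and the HAM-D6 is rated separately by blinded central raters. Power, the significance level and the primary conclusion do not depend on the CGI-I.

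**What to change.** Replace the sentence in the CGI-I row of Section 5.2 with an instruction such as: *rate the total change in the participant's condition since baseline, whether or not you believe it is due to the study app.* This agrees with the anchors and with the ordinal model, and it can be answered by a blinded rater. Then check that the Protocol Supplement, the rating form and the rater training use the same wording.

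Under Section 13 a permanent change needs a written amendment and IRB approval before it takes effect, so the cost is minor but not nil. If ratings have already been made under the current wording, record the date of the change so that ratings before and after it can be told apart. The change is low priority and could be combined with another amendment.

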5.3 SAFETY ASSESSMENTS

To further manage risk in this clinical trial of WB001, the study will incorporate validated psychometric assessments conducted at regular intervals to monitor for worsening symptoms and/or the development of suicidal ideation. The study population will only include participants with mild-moderate depression (inclusion

Sponsor Name: Woebot Health

Protocol Number: WB001-001

criterion) and specifically excludes patients with severe depression and prior history of treatment-resistant depression (exclusion criteria). The study will also appropriately monitor worsening of symptoms through the following:

- a. Administering the C-SSRS at BL, Week 4, and Week 8
- b. Administering the PHQ-9 (item #9), EPDS (item #10), and HAM-D (item #3) at BL, Week 4, and Week 8
- c. This protocol continues to adhere to FDA guidance that appropriate assessments, such as assessing for AE/SAEs and administering the C-SSRS, should occur at each planned visit wherein the other clinical assessment will be administered. Thus, the assessment schedule for the C-SSRS mirrors that of the HAM-D.
- d. Study participants are welcome to initiate contact anytime throughout the duration of the study with their site. If the contact is attributable to safety reasons, then an Unplanned Visit would ensue, wherein qualified study personnel would follow-up with the participant in a timely manner, and if needed administer the C-SSRS.

Scenarios that would trigger an escalation for an Unplanned Visit include:

- [REDACTED]
- [REDACTED]
- [REDACTED]

ADVERSE EVENTS

At each telehealth visit, the PI and site staff will evaluate participants for any changes that could indicate AEs. Participants with AEs will be followed, recorded in the EDC and reported in line with the procedures described in Section 7. Participants will be instructed to contact the study site if any new symptoms occur in between the weeks of telehealth visits. The CIR is responsible for detecting, documenting, and recording any potential safety events based on the administered HAM-D (i.e., score of ≥ 2 on HAM-D17 item #3) that may meet the definition of an AE or SAE, but the investigator will remain responsible for following up on all safety events to confirm if an AE/SAE has occurred and determine the appropriate course of action. The method of recording, evaluating, and assessing causality of AEs and SAEs and the procedures for completing and transmitting SAE reports are provided in Section 7.

SUICIDAL IDEATION AND BEHAVIOR RISK MONITORING

[figure not shown]
Sponsor Name: Woebot Health

Protocol Number: WB001-001

The study design includes assessment of suicidal ideation as described. All participants will meet with the investigator or qualified site staff at Baseline, Week 4, and Week 8 during a telehealth visit, and will be administered psychometric tests (i.e., C-SSRS and HAM-D item #3) to assess suicidal ideation.

C-SSRS

The clinician-administered C-SSRS is a measure used to identify and assess individuals at risk for suicide (The Columbia Lighthouse Project/Center for Suicide Risk Assessment, 2019). The C-SSRS measures four constructs: the severity of ideation, the intensity of ideation, behavior, and lethality. The C-SSRS is made up of ten categories, with binary responses (Yes or No) to indicate presence or absence of the behavior, and the outcome is a numerical score obtained from these categories. The C-SSRS will be administered by the investigator or qualified site staff during telehealth visits at baseline, Week 4, and Week 8 to monitor for potential onset of suicidal ideation. If a score on the C-SSRS raises a safety concern, i.e., 'yes' on questions 4 or 5, or answer 'yes' to "actual attempt" question in "Suicidal Behavior" section the site-based rater will immediately contact the PI/sub-investigator to ensure that the investigator urgently conducts an assessment of this participant to determine the appropriate actions to take and disposition of the participant. Similarly, if a safety concern is raised due to a score submitted through a CIR administered structured clinical interview (a score of ≥ 2 on the HAM-D17 item #3) or self-report ePROs (a score of ≥ 2 on item #9 of PHQ-9 and/or score of > 2 on item #10 of EPDS), an electronic system at the sites will notify the investigator to review each incident and follow up with the participant within 24 hours to determine if any action is required. If so, the investigator will be responsible for administering a formal assessment using the C-SSRS, if deemed necessary.

Sponsor Name: Woebot Health

Protocol Number: WB001-001

[REDACTED]

[REDACTED]

[REDACTED]

[REDACTED]

[REDACTED]

[REDACTED]

PREGNANCY AND BREASTFEEDING

Although pregnancy is exclusionary and a participant who becomes pregnant during the study will be withdrawn, there are no protocol-specific requirements for pregnancy testing or contraceptive use. Changes in pregnancy status will be completed via self-report during key assessment visits. There are no precautions regarding breastfeeding during the study because the intervention is not a medicinal product.

Details of all pregnancies in female participants will be collected after the start of study intervention and until end of Week 8.

If a pregnancy is reported, the site staff and/or investigator will record pregnancy information in the EDC and submit it to the Sponsor within 24 hours of learning of the female participant's pregnancy and initiate withdrawal from the study.

12-LEAD ELECTROCARDIOGRAM, VITAL SIGNS, AND PHYSICAL EXAMINATIONS

Sponsor Name: Woebot Health

Protocol Number: WB001-001

These assessments are not scheduled as part of the study; however, if deemed necessary, the investigator may arrange for participants to be referred for medical evaluation.

UNSCHEDULED VISITS

Study participants are welcome to initiate contact anytime throughout the duration of the study with their site. If the contact is attributable to safety reasons, then an Unscheduled Visit would ensue, wherein the qualified study personnel would follow-up with the participant, and if needed administer the C-SSRS.

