Participants will attend a mid-study and EOT (at Week 4 and Week 8) telehealth visit with a CIR, to be assessed based on the HAM-D, a validated standard clinician-rated and participant-rated outcome scales for PPD. Any AE/SAE raised during CIR-administration of HAM-D, will be raised to the PI or qualified designee for final determination on appropriate course of action. At Week 4 and Week 8 the PI or qualified site staff will

Sponsor Name: Woebot Health

[figure not shown]
Protocol Number: WB001-001

administer the C-SSRS, evaluate for concomitant medications/therapy, pregnancy status, and safety throughout the duration of the trial.

At Week 4 and 8, participants will be prompted to complete several online self-report assessments (e.g., EPDS, PHQ-9, MIBS, GAD-7 and PGI) within 3-days prior to or 3-days after the visit date. The same assessment steps in Week 4 will apply to Week 8 (EOT) visits, with the addition that at Week 8 participants will receive instructions about how to uninstall the app and will go through other end-of-study procedures.

Not including the referral period and potential for participants to complete the last self-reported assessments 3 days after the week 8 visit, the duration of study participation is 8 weeks. [Figure 3](#) shows the overall Study Schematic.

Figure 3. Study Schematic

[figure not shown]
[figure not shown]

Sponsor Name: Woebot Health

Protocol Number: WB001-001

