5.2 EFFICACY ASSESSMENTS

The following table summarizes the efficacy and safety assessments that will be used for primary, secondary, and exploratory endpoints during the study period.

Assessment	Endpoint Type	Definition
HAM-D	Primary	
 The HAM-D17 is a 17-item clinician-rated measure of depression (Hamilton, 1960). The HAM-D6 is a subset of the HAM-D17 that assesses 6 core items associated with major depression: depressed mood (item 1), feeling of guilt (item 2), difficulty performing work and activities (item 7), motor retardation (item 8), psychic anxiety (item 10), and somatic symptoms (general, i.e., low energy and bodily pain) (item 13) Item 13 is scored 0 to 2 (0 = none/absent to 2 = most severe) and all other items are scored 0 to 4 (0 = none/absent to 4 = most severe). Total score ranges from 0 to 22 and a higher score indicates greater severity of depression. The HAM-D is commonly used for diagnostic purposes in research, and structured clinical interviews such as this are recommended to formally diagnose clinical depression (Norhayati et al., 2015). The HAM-D17 will be administered at baseline via the Structured Interview Guide for the Hamilton Depression Rating Scale (SIGH-D 17-item HAM-D), at Week 4, and Week 8 to derive HAM-D6
EPDS	Secondary	
 A brief self-report questionnaire used as a screening tool to identify patients who are at risk for perinatal depression (Cox et al., 1987; Wisner et al., 1994). The 10-item scale assesses depression criteria (including anhedonia, anxiety, sleep disturbance, and suicidal ideation) in the past seven days. Each item has four ordinal response options, yielding a total score of 0 to 30 where a higher score denotes greater depression (values ≥ 10 denote possible depression). The EPDS is a widely used measure with demonstrated reliability and validity for the assessment of depression (Yawn et al., 2009; Zhong et al., 2014), and is also routinely used in clinical care practice for the assessment of patients with PPD. The EPDS will be administered at baseline, Week 4, and Week 8.

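### EPDS item 10 alerts the investigator only at its maximum of 3, so under the visible rules a score of 2 entered 1 to 3 days after the Week 8 visit can pass without an alert or a later scheduled C-SSRS (cheap fix, low priority)

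*Combined protocol and SAP*

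**What the plan says.** Section 5.3 (C-SSRS) lists the scores that make the site's electronic system notify the investigator, who then follows up within 24 hours. For the self-report forms the trigger is a "score of ≥ 2 on item #9 of PHQ-9 and/or score of > 2 on item #10 of EPDS". For the rater's interview it is a "score of ≥ 2 on HAM-D17 item #3". The EPDS row of Appendix 3 repeats the EPDS rule: "If safety flag is raised due to score of >2 on item #10, EPDS". The PHQ-9 row repeats its own cut-off of 2 or more.

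Section 5.2 describes the ten-item EPDS: "Each item has four ordinal response options, yielding a total score of 0 to 30". It covers several symptoms "and suicidal ideation) in the past seven days". The same table scores each PHQ-9 item from 0 to 3, with a two-week recall.

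The C-SSRS and HAM-D17 are scheduled at baseline, Week 4 and Week 8. The self-report forms have a window of 3 days either side of the visit, and Section 3.1 allows for the "potential for participants to complete the last self-reported assessments 3 days after the week 8 visit". The Appendix 3 notes say that "AEs/SAEs should be recorded until the EOT visit". Section 7.3 does not oblige investigators to look actively for events once participation has ended.

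**The concern.** The Safety Aim in the Synopsis names EPDS item 10 as one of the tools for identifying adverse events. Its alert ignores every answer except the highest one, whereas the suicidality item of the PHQ-9, on the same 0 to 3 range, alerts on the top two.

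At most times this matters little, because an interview is done on the same day, soon afterwards or at the next visit. The exception is a Week 8 form completed after the Week 8 visit. If item 10 is 2 and PHQ-9 item 9 is below 2, the visible rules send nothing to the investigator, and no scheduled assessment remains that could pick it up. The Benefit/Risk Assessment lists losing access to the app at Week 8 as a possible source of brief stress, and this window follows directly.

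What is at stake is participant safety, not the treatment comparison.

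**Working it through.** **Inputs**
- EPDS: 10 items, four options each, total 0 to 30 (Section 5.2).
- PHQ-9 items: 0 to 3 (Section 5.2).
- Alerts: EPDS item 10 > 2; PHQ-9 item 9 ≥ 2 (Section 5.3 and Appendix 3).
- Visits: Day 28 ± 3 and Day 56 ± 3; self-report forms within 3 days of the visit (Appendix 3).
- Planned sample: 210 (Synopsis).
- Assumed, not in the documents: 0.5% to 5% of forms have EPDS item 10 of 2 with PHQ-9 item 9 of 0 or 1; one third of forms are late.

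**Step 1: which scores alert.** Item maximum = 30/10 = 3, so items take the values 0, 1, 2, 3. The EPDS rule is met by 3 only, the PHQ-9 rule by 2 and 3. Of the 16 pairs of scores, those with EPDS item 10 of 2 behave as follows:

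| PHQ-9 item 9 | Alert now | Alert with EPDS ≥ 2 |
|---|---|---|
| 0 | no | yes |
| 1 | no | yes |
| 2 | yes, through PHQ-9 | yes |
| 3 | yes, through PHQ-9 | yes |

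Lowering the cut-off adds exactly two pairs, (2, 0) and (2, 1).

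**Step 2: which forms have no interview after them.**
- Baseline: all assessments are done on one day, so there is no gap.
- Forms completed before a visit: the visit interview follows.
- Late Week 4 forms: completed on Day 25 + 1 = 26 to Day 31 + 3 = 34. The next C-SSRS is on Day 53 to 59, which is 53 − 34 = 19 to 59 − 26 = 33 days later. If both visits are on their nominal days, it is 56 − 31 = 25 to 56 − 29 = 27 days.
- Late Week 8 forms: completed on Day 53 + 1 = 54 to Day 59 + 3 = 62. No later C-SSRS is scheduled.

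**Step 3: how much the Week 8 interviews already cover.** With seven-day recall and a form 1 to 3 days late, 7 − 3 = 4 to 7 − 1 = 6 recall days precede the visit. Only 1 to 3 days are new.

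**Step 4: size of the Week 8 gap at the assumed rates.**
- Every form late: 210 × 0.5% = 1.05; 210 × 5% = 10.5.
- One third late (70 forms): 70 × 0.5% = 0.35; 70 × 5% = 3.5.

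These counts err on the high side at those rates, because they do not remove women whose Week 8 interview had already raised a concern. The base of 210 is not a ceiling: the sample size may be re-estimated (Section 9.9) and withdrawn participants may be replaced (Section 4.6).

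**Step 5: extra reviews caused by each remedy.**
- Cut-off ≥ 2 on all forms: 210 × 3 = 630 forms; 630 × 0.5% = 3.15; 630 × 5% = 31.5.
- Only late Week 4 and Week 8 forms: at most 210 × 2 = 420; 420 × 0.5% = 2.1; 420 × 5% = 21. With one third late (140 forms): 0.7 to 7.

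**The case against.** The strongest reply is that the text needed to settle the matter is redacted. The scenarios for an Unplanned Visit, the text after the C-SSRS paragraph in Section 5.3, and the escalation triggers in the Appendix 3 notes are all blacked out. One of them could catch a late score of 2. This stands as a limit on any statement about how many women would be missed. It does not remove the point, because the item 10 cut-off itself is visible and stated twice.

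Second, the cut-offs need not match. The EPDS and PHQ-9 differ in recall period, HAM-D17 item 3 is rated by a clinician, and the documents give no response wording for EPDS item 10. That is right. A reader might infer that > 2 is a slip for ≥ 2, or that a 2 on one scale carries the same risk as a 2 on another. The documents support neither: the cut-off is used consistently, and nothing equates the scales.

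Third, other protection exists. The Week 8 interviews cover most of the recall period. Section 4.2 excludes women with ideation with plan and intent in the current episode. Participants are told to report new or worsening symptoms, and "If the contact is attributable to safety reasons, then an Unplanned Visit would ensue". All have clinician-supervised usual care. This makes the gap narrow but does not close it, since these routes after Week 8 depend on the woman speaking up rather than on the answer she has already given. The follow-up after end of treatment in Section 7.3 applies only to events already identified.

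Fourth, the lack of a later C-SSRS applies to every late Week 8 form, not only to this item. That is true. The remedy for an informative late answer is an alert, and that is what the EPDS rule withholds at 2.

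**Conclusion.** The point holds as a low-priority safety improvement. Under the visible rules the EPDS item 10 alert fires only at the maximum, without a stated reason. A score of 2 with PHQ-9 item 9 of 0 or 1, entered 1 to 3 days after the Week 8 visit, produces no self-report alert and has no scheduled C-SSRS after it.

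Its size cannot be computed from the documents. The figures of about 1 to 10 women (all forms late) or 0.4 to 3.5 (one third late) rest entirely on the assumed rates, the assumed share of late forms and a sample of 210.

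A reader might go further and conclude that women at risk will be left without follow-up, or that the trial result is affected. Neither follows. A redacted trigger may reach some of these women, and the Week 8 interviews cover 4 to 6 of the seven recall days. Both arms use the same rules, so no between-arm bias is claimed.

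**What to change.** In Section 5.3 (C-SSRS) and in the EPDS row of Appendix 3, change the item 10 cut-off from > 2 to ≥ 2, and set the electronic alert to match.

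As a minimum, if > 2 is intended, keep it and add a rule that any item 10 score of 2 on a form completed after the visit goes to the investigator for review within 24 hours.

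The change takes two wording edits and one system setting, with no new scheduled visit or assessment. The running cost is about 3 to 32 extra 24-hour reviews over 630 forms at the assumed 0.5% to 5%, and more if the sample size is increased. Some reviews may lead to an unscheduled C-SSRS. The minimum version costs about 2 to 21 reviews if every Week 4 and Week 8 form were late, and about 1 to 7 if one third were.
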